Hypotheses: The effects of infant age of egg introduction and frequency of egg intake will vary by the child outcome of interest (**Hypothesis 1**). We predict a non-linear association between age of egg introduction and the average probability of multiple child outcomes (i.e., stunting, underweight, obesity, high risk of metabolic syndrome, food allergy, and cognitive delay), with the optimal age being a time point that falls between 6-12 months (**Hypothesis 2**). We also predict a non-linear association between frequency of infant egg intake and the average probability of multiple child outcomes, with the optimal frequency being 2-4 times per week (**Hypothesis 3**).

3) Project Design:

Sample/Data. We propose a 2-year study to examine the extent to which two important aspects of infant egg consumption (i.e., age of introduction and frequency of intake) influence physical growth, obesity, cardio-metabolic health, risk of food allergy, and cognition development in mid-childhood and adolescence. Guided by a life course framework (**Figure 1**), we will use existing secondary data from two US longitudinal birth cohorts that tracked mother-child dyads from pregnancy to adolescence: 1) **Project Viva** (1999-present, N=2,128 newborns) that followed children at delivery, 6 months (m), 1 year (y), 2 y, 3 y, 4 y, 5 y, 6 y, 7 y, 8 y, 9 y, 10 y, 11 y, 12-13 y, 14 y, and 15 y of child age,³⁷ and 2) **Infant Feeding Practices Study II** (IFPS II, 2005-2012, N=3,033 newborns) that followed children at neonatal (1 m), 2 m, 3 m, 4 m, 5 m, 6 m, 7 m, 9 m, 10 m, 12 m, and 6 y of child age.^{38,39} The PI has access to both datasets, and has 3 publications on infant nutrition, early childhood diet, growth, and obesity using Project Viva^{40,41} and IFPS II⁴² data since 2014. These two studies have a similar study design and complementary measures of child outcomes, which provide a unique opportunity for comprehensive analysis on the health effects of infant egg consumption and also external replication of findings.

Exposure measures (infant egg consumption). We will focus on age of introduction and frequency of intake as the key exposure measures of infant egg consumption, because evidence

Infant Egg Consumption | Child Health and Cognition | Clinical Guidelines

Figure 1. Conceptual framework on effects of infant egg consumption

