For **Aim 1 (infant age of egg introduction)**, we will first classify the infants based on their age of egg introduction: never, <2 m, 2-3 m, 4-5 m, 6-8 m, 9-11 m, and 12 m. Then we will compare their physical growth, obesity, cardio-metabolic risk profile, risk of food allergy, and cognition test scores in mid-childhood and adolescence using Chi-square tests (categorical outcomes) or ANOVA tests (continuous outcomes). We will fit multivariable linear (continuous outcomes) or logistic (binary outcomes) regression models with fractional polynomial functions of infant age of egg introduction, adjusted for significant confounders. Both linear (e.g., earlier introduction, high probability of the outcome) and non-linear (e.g., threshold effect) associations will be tested. The non-linear trend will be examined through visualization of scatter plots and statistical tests of polynomial term of infant age of egg introduction in the regression models. If the polynomial terms of age are not significant, we will drop it and consider the association to be linear.

Then, we will fit a mixed effect model (SAS PROC MIXED) for continuous outcomes (height z-score and BMI z-score) and a generalized linear mixed effect model (SAS PROC GLIMMIX) for binary outcomes (obesity and diagnosis of food allergy) that were measured repeatedly across multiple age points. The mixed effect model will include random intercepts, random slopes for age effects, and autoregressive variance-covariance matrix across different time points. Independent variables in the model will include infant age of egg introduction, outcome age point (mid-childhood and adolescence), the 2-way interaction term (infant age of

egg introduction × outcome age point), and significant covariates. The 2-way interaction term quantifies the extent to which infant age of egg introduction can affect the specific outcome. The PI has experience with using mixed effect models for examine child growth measures and multiple publications in this area.^{51,52}

For **Aim 2 (frequency of infant egg intake)**, we will first classify the infants based on their frequency of egg intake: never, <once/week, once/week, 2–4 times/week, nearly daily or daily, and ≥ 2 times/day. Then, we will use similar analytic methods mentioned above for Aim 1 to compare their health and developmental outcomes.

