In addition, we will create an **average probability of multiple child outcomes** to balance across different aspects of child health and development using the methods published by Oken et al.⁵³ for identifying the lowest-risk exposure level when multiple outcomes are considered. Specifically, we will focus on 6 binary child outcomes including stunting, underweight, obesity, high risk of metabolic syndrome (e.g., z score $\geq 95^{\text{th}}$ percentile), food allergy, and cognitive delay (e.g., standardized cognition score < 85 points). We will use estimates from aforementioned logistic models to generate predicted probabilities of each of the 6 adverse outcomes when the independent variable of infant egg consumption (i.e., age of egg introduction or frequency of egg intake) varies across the observed range within our study sample. We will calculate the average probability of the 6 outcomes, assuming these outcomes are equally important. We will identify the lowest-risk infant egg consumption when the corresponding average probability of the 6 adverse outcomes is the lowest.

We will handle missing data with Multiple Imputation.⁵⁴ Specifically, we will first generate 20 replicates of datasets (PROC MI in SAS) with imputed values for missing data on infant egg consumption, child outcomes, and significant covariates, based on a bayesian approach. The 2nd stage is to use standard statistical methods (e.g., Linear Regression) to fit the model of interest to examine the association between infant egg consumption and the specific outcome within each of the 20 imputed datasets. The 3rd stage is to pool the analytic results from all 20 imputed datasets to get the average estimates of the association (PROC MIANALYZE). The PI has experience with Multiple Imputation for large datasets.⁵⁵

All our analyses will be first conducted among boys and girls separately to examine the potential sex differences. A formal interaction test will be conducted by including the interaction term of egg consumption and sex into the regression models. If the interaction term is significant, sex-stratified results will be reported. Otherwise, sex-pooled analytic results will be reported.

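### Replacing a curve by a straight line whenever its polynomial term is non-significant can push the estimated lowest-risk age to an end of the range and miss an interior optimum when curvature is weak

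*Combined protocol and SAP*

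**What the plan says.** All references are to the combined protocol and SAP.

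- **Data analysis, Aim 1.** The plan starts from "regression models with fractional polynomial functions of infant age of egg introduction", looks at scatter plots and tests the polynomial terms. The rule is then: "If the polynomial terms of age are not significant, we will drop it and consider the association to be linear". No significance level is given for this test.
- **Data analysis, average probability of multiple child outcomes.** "We will use estimates from aforementioned logistic models to generate predicted probabilities of each of the 6 adverse outcomes", while the exposure "varies across the observed range within our study sample". Then: "We will calculate the average probability of the 6 outcomes, assuming these outcomes are equally important". The exposure with the lowest average is named as lowest-risk. No interval for that exposure is described, and no sensitivity analysis that keeps the curve.
- **Hypotheses.** Hypothesis 2 predicts a non-linear association, "with the optimal age being a time point that falls between 6-12 months".
- **Range of ages.** Aim 1 lists the categories "never, <2 m, 2-3 m, 4-5 m, 6-8 m, 9-11 m, and 12 m"; the opening summary ends the list at 12 m or later. How infants never given egg enter a continuous age term is not stated.

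**The concern.** The rule reads failure to reject linearity as linearity. For describing one outcome that is a common simplification. Here the simplified model goes on to a step whose purpose is to find a turning point, and a single straight line on the logit scale has none inside the range. Each outcome whose curvature misses significance therefore adds a slope, and no curvature on the logit scale, to the average.

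At stake is the study's headline result, the recommended age of introduction. If curvature is real but weak, the reported age may be the earliest or latest age in the data, and the plan gives the reader no interval that would show how uncertain that is.

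**Working it through.** **1. The plan's own figures.** Statistical Power gives detectable odds ratios of 1.46 (N=2,128) and 1.38 (N=3,033) at type 1 error 0.05 and power 0.8. Assume a two-sided test, a reference risk of 10% and a 1:1 split of the whole cohort; none of these is stated.

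- p2 = 0.10·OR / (0.90 + 0.10·OR). For 1.46: 0.146/1.046 = 0.1396. For 1.38: 0.138/1.038 = 0.1329.
- n per group = [1.96·√(2p̄(1−p̄)) + 0.842·√(p1(1−p1) + p2(1−p2))]² / (p2−p1)², which gives 1,056 and 1,487.
- Totals: 2 × 1,056 = 2,112 against 2,128 (power 80.3%), and 2 × 1,487 = 2,974 against 3,033 (power 80.8%).

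The figures reproduce, but they describe a contrast of two groups. They say nothing about power for a polynomial term.

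**2. The mechanism.** If logit p = α + βa, then dp/da = β·p(1−p), which never changes sign, so the minimum is at an end. For the average of six such curves the derivative is (1/6)·Σ βk·pk(1−pk), which can be zero inside the range if the slopes differ in sign. Each curve is convex when p is below 50%, so that point is a minimum. With assumed risks, three rising and three falling outcomes at OR 1.05 per month give a minimum at 9.1 m, and four rising and two falling at OR 1.10 give 7.75 m. Another four-against-two pattern at OR 1.05 puts it at 12.0 m, an end. Opposing slopes can hold the minimum inside, but need not.

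**3. Power of the curvature test.** Ages follow the IFPS II figures under Age of egg introduction: 1.7% by 6 m and 63.0% by 12 m, so 63.0 − 1.7 = 61.3% between and 37% later or never. Take one outcome at 5-10% risk, quadratic with its minimum at 8.5 m and OR 1.46 at 3.5 m either side, N=2,128. Power is 34-45% if infants not introduced by 12 m are excluded and 85-97% if they are placed at 12-15 m. At OR 1.2 it is 12% and 28-46%. The answer depends on a coding choice that the plan leaves open.

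**4. Effect on the estimated optimum.** Assumptions: six independent outcomes with prevalences 2.3, 5, 15, 5, 8 and 10%; logit pk(a) = αk + b(a−9)² with b = ln(1.15)/9 = 0.0155; the age distribution above on 3-15 m; a quadratic standing in for the fractional polynomial, kept only if p<0.05 (rule) or always (kept). Ranges are the spread over repeat runs.

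| Setting (OR 1.15 at 3 m) | Result counted | Rule | Kept |
|---|---|---|---|
| N=2,128, ages 3-15 m | outside 6-12 m | 16-23% | 0-1% |
| N=1,064 (one sex), 3-15 m | outside 6-12 m | 34-35% | 3-5% |
| N=2,128, range stops at 12 m | outside 6-12 m | 9-11% | 1-4% |
| same | at an end | 38-43% | 3-4% |

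N=1,064 is 2,128/2, since all analyses are first run by sex. At OR 1.46 and N=2,128 the two approaches nearly agree.

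**5. A second set of assumptions.** Risks of 3, 5, 12, 5, 6 and 16%, optimum at 8.5 m, OR 1.2 at 3.5 m, later infants excluded, N=2,128. Estimates at an end fall from 33% (rule) to 5% (kept) with six curved outcomes, and from 48% to 20% with only two. At OR 1.46 and full N, across the age settings tried, the rule gives 0-2% at an end with six curved outcomes; with fewer curved outcomes included, the range is 0-19% under the rule and 0-6% kept.

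**6. The other side of the trade.** Design of step 4, N=2,128, but truly linear risk (all six rising, OR 1.15 per 3 m). A false interior optimum appears in about 54% of data sets with the curve kept and 12-15% under the rule; it lies inside 6-12 m in 21% against 8%. With no association at all, an interior optimum appears in about 61% against 30%, best read as roughly a doubling.

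**The case against.** The strongest reply is that the rule protects against the error Hypothesis 2 invites. A curve that is always kept will often turn somewhere, so it produces the predicted kind of answer more often when that answer is false (step 6). This stands. It means that the price of keeping the curve is more than somewhat wider intervals, and that the point estimate must not be reported alone.

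Second, step 4 assumes all six outcomes share one optimum, whereas Hypothesis 1 expects effects to differ by outcome. This also stands: with two curved outcomes, keeping the curve still left 20% at an end. The gap between the approaches remains.

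Third, OR 1.15 is smaller than anything in Statistical Power, and sex-specific results are reported only if the interaction is significant. That limits where the harm falls. But the stated odds ratios concern two groups, and the plan never says what curvature it could detect.

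A reader might infer that the rule always drives the answer to an end, or that the plan cannot find an interior optimum. The documents do not support that: the rule acts outcome by outcome, one retained curve can hold the minimum inside, and so can opposing slopes. Nor can results at N=3,033 be carried over to the six-outcome average, because metabolic and cognition measures are described only for Project Viva.

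**Conclusion.** The concern holds in limited form. The rule passes models chosen by a test of unstated power to a search for a minimum. It can miss a true interior optimum when curvature is weak, few outcomes are curved, or models are fitted by sex. The size is that of step 4: at N=2,128 and OR 1.15, roughly one data set in five or six outside the hypothesised window on a 3-15 m range. If the range stops at 12 m, the upper end itself lies within 6-12 m. Fewer estimates then leave the window, yet about two in five still sit at an end although the true optimum is 9 m. With strong curvature in all six outcomes at full N the effect is negligible.

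On balance keeping the curve is better. The mean excess risk at the chosen age was lower by about 0.7 percentage points when curvature was weak but real, and higher by about 0.2 when the truth was linear.

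Prevalences, curvature, independence of outcomes and ages beyond 12 m are assumptions; covariates, missing data and attrition were ignored. The six-outcome average appears possible only in Project Viva, so N is at most 2,128. This is a change that should be made; it does not invalidate the design.

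**What to change.** 1. In the average-probability step, pre-specify one flexible form (for example a second-degree fractional polynomial) for all six outcomes and keep it whatever the p-value. State the age range searched and how infants not introduced to egg are coded.
2. Report the non-linearity test as a result rather than a selection rule. In single-outcome models, describe a non-significant test as no clear departure from linearity.
3. Report a bootstrap interval for the lowest-risk age, and claim an interior optimum only if that interval supports it.
4. Show the linear or test-selected fit as a sensitivity analysis.

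Aim 2 borrows Aim 1's methods, so the wording should cover both; no figures were worked out for frequency.

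**Cost.** A few sentences in the plan and more computing, since the bootstrap must be combined with the 20 imputed data sets. The statistical cost is more false interior point estimates when the truth is linear or null, and wider intervals when it is linear. Keeping the curve does not remove the uncertainty about the optimum, so item 3 cannot be left out.

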Statistical Power. We expect sufficient statistical power for our hypothesis-driven data analyses for both Aims, because 1) the 2 cohorts had relatively large sample sizes (N=2,128 for Project Viva and N=3,033 for IFPS II), which are sufficient to detect a small odds ratio (1.46 for Project Viva, 1.38 for IFPS II with type 1 error being 0.05 and power being 0.8) of binary child outcomes (e.g., food allergy) between infants with different egg consumption (e.g., egg introduced at ≥ 12 m vs 6-8 m) or a small effect (effect size=0.054 for Project Viva, 0.051 for IFPS II) of infant egg consumption on continuous outcomes (e.g., intelligence score); 2) most child outcomes were measured repeatedly; 3) infant egg consumption varied largely within cohorts.

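### The mixed-model interaction of egg introduction with outcome age is read as the egg effect, but it is only the difference between the effects at two ages

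*Combined protocol and SAP*

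**What the plan says.** The combined protocol and SAP, section 3) Project Design, Data analysis, sets out two layers of analysis for Aim 1.

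- **Separate regressions.** "We will fit multivariable linear (continuous outcomes) or logistic (binary outcomes) regression models", with fractional polynomials of age at egg introduction.
- **Repeated-measures models.** A linear mixed model is planned for height and BMI z-scores, and a "generalized linear mixed effect model (SAS PROC GLIMMIX) for binary outcomes (obesity and diagnosis of food allergy"). Their fixed effects are listed as follows: "Independent variables in the model will include infant age of egg introduction, outcome age point (mid-childhood and adolescence), the 2-way interaction term", plus covariates.

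The plan then interprets one term only: "The 2-way interaction term quantifies the extent to which infant age of egg introduction can affect the specific outcome". For these models it mentions no age-specific contrast, no average over ages and no joint test.

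For Aim 2 it says that "we will use similar analytic methods mentioned above for Aim 1 to compare their health and developmental outcomes", so the same reading carries over to egg frequency. The lowest-risk calculation draws on the other layer: "We will use estimates from aforementioned logistic models to generate predicted probabilities of each of the 6 adverse outcomes".

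**The concern.** The objective is the association of infant egg consumption with later outcomes. The sentence assigns that role to a coefficient that measures something else: how far the association changes between mid-childhood and adolescence. Both ages come after the exposure, so there is no pre-exposure time point against which a change over time would represent the effect. A lasting influence of infant diet, the same at both ages, sits entirely in the main effect and cancels out of the interaction.

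An analyst who follows the sentence could report no effect from the mixed model for a stable association, and an effect where the average association is nil. Either result could appear to contradict the separate regression for the same outcome. Four outcomes are involved, in both aims.

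**Working it through.** The sentence carries no figure, so there is none to reproduce. The check is algebraic; the numbers below only illustrate it.

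**Inputs.** The model terms and the two outcome ages come from Data analysis, Aim 1. The sample size of 2,128, the type 1 error of 0.05 and the odds ratio (OR) of 1.46 come from Statistical Power, which claims enough children to "detect a small odds ratio (1.46 for Project Viva, 1.38 for IFPS II with type 1 error being 0.05 and power being 0.8"). The 1.46 is borrowed only as a size. The patterns over age are assumed.

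**Model.** Code age as 0 for mid-childhood and 1 for adolescence:

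logit P = b0 + bE·egg + bA·age + bI·egg·age + random effects

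- Egg effect in mid-childhood: bE
- Egg effect in adolescence: bE + bI
- Average of the two: bE + bI/2
- Interaction: bI = (bE + bI) − bE, the difference

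Hence exp(bI) = OR(adolescence) / OR(mid-childhood), and the average OR on the log scale is √(OR(mid-childhood) × OR(adolescence)).

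| Assumed pattern | OR mid-childhood | OR adolescence | exp(bI) | Average OR |
|---|---|---|---|---|
| Constant | 1.46 | 1.46 | 1.46/1.46 = 1.00 | 1.46 |
| Constant, large | 3.00 | 3.00 | 3.00/3.00 = 1.00 | 3.00 |
| Fading | 1.46 | 1.00 | 1.00/1.46 = 0.68 | √1.46 = 1.21 |
| Growing | 1.00 | 1.46 | 1.46/1.00 = 1.46 | √1.46 = 1.21 |
| Reversing | 1.208 | 0.828 | 0.828/1.208 = 0.68 | 1.00 |

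The same ratio (0.68) goes with average ORs of 1.21 and 1.00. The same average (1.21) goes with ratios of 0.68 and 1.46. The interaction therefore does not determine the effect. The main effect alone does not either: under 0/1 coding in the fading case it is 1.46 or 1.00, depending on which age is the reference.

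**Continuous outcomes.** Assume a standardised exposure, residual variance 1 and within-child correlation ρ of 0.3, 0.6 or 0.8, with N = 2,128 and a two-sided 5% test. The standard errors are 1/√N = 0.0217 for each age, √(2(1−ρ)/N) for the interaction and √((1+ρ)/(2N)) for the average.

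| Effect (mid-childhood, adolescence) | Interaction | Rejection rate, interaction | Power, each age | Rejection rate, average |
|---|---|---|---|---|
| 0.10, 0.10 | 0 | 5% | 99.6% | at least 99.8% |
| 0.061, 0.061 | 0 | 5% | 80% | 84% to 94% |
| 0.05, −0.05 | −0.10 | 97% to over 99.9% | 64% | 5% |

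**Check of the constant case by simulation.** Assumed: a random-intercept logistic model with intercept SD 1.5, b0 = −2.0, bA = 0.1, two equal exposure groups, 2,000 children seen at both ages, 500 runs.

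- True OR 1.46 at both ages: median ratio of odds ratios 1.003, interaction significant in 5.6% of runs, median average OR 1.459.
- True OR 3.00 at both ages: 1.007, 6.8% and 2.992.

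The Monte Carlo standard error of the percentages is √(0.05 × 0.95/500), about 1 point, so both are compatible with 5%.

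**Other forms of the model.** If egg age enters as categories or polynomial terms, the interaction is a set of such differences. If outcome age is continuous, it is the effect on the slope over age. The plan's reading would be right only if the egg main effect were left out, with egg nested within age, and the plan lists that main effect.

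**Cohort.** The text does not say which cohort supplies these models. The IFPS II schedule ends "9 m, 10 m, 12 m, and 6 y of child age". IFPS II has repeated measures in infancy and at 6 y, so a mixed model with other age points is possible there. A contrast of mid-childhood with adolescence is not.

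**The case against.** The strongest reply is that this is one loose sentence about a sound model. The main effect is in the model, so every effect of interest can be recovered from the same fit. The separate regressions cover the same outcome domains and estimate the association directly. Hypotheses 2 and 3 concern the average probability, which does not use this term. No rule says that the interaction alone decides, and the multiple-imputation text speaks of pooling estimates of the association. All of this stands, and it limits the harm to misreading. It does not make the sentence right, and nothing elsewhere corrects it.

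A second reply is that change over age is a legitimate target in a longitudinal model with random slopes, and that the sentence is shorthand for it. Such a target is legitimate, but the sentence claims the extent of the effect, not its change.

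A third reply concerns coding. With ages coded −1/2 and +1/2, the main effect is the average over ages. That is correct, and the remark about the reference age depends on 0/1 or default CLASS coding in the SAS procedures the plan names. Under either coding the interaction is still the difference.

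Finally, an average over ages can hide a reversal. That is true of the average alone, which is why age-specific effects should be reported beside it.

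**Conclusion.** The concern holds. The interpretation given to the interaction is wrong as written for all four mixed-model outcomes and, through the shared methods, for Aim 2. The core result is an identity that needs no assumed input: the interaction is zero for any effect equal at both ages. In that case its test rejects at the nominal 5%, while in the illustration each age-specific effect has 80% to 99.6% power. Those power figures and the OR patterns rest on the stated assumptions and are not estimates for this study.

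The correction should be made, but its reach is limited. The planned model, the separate regressions and the lowest-risk calculation are not in question.

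**What to change.** Replace the sentence with wording such as:

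> The effect of egg introduction is estimated at each outcome age as main effect plus interaction (the interaction being zero at the reference age), and averaged over ages; the interaction tests only whether the association differs by outcome age.

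Report the age-specific effects beside the average. Use the same wording for egg frequency in Aim 2. State that the contrast of mid-childhood with adolescence is estimated in Project Viva only, because IFPS II follow-up ends at 6 y.

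The cost is a small change of plan wording and a few contrast statements in the SAS models already planned. No new data and no change of model are needed.

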supports their potential influences on child health and development⁴³. We recognize that other aspects of infant egg consumption such as different egg fractions (i.e., white vs yolk⁴⁴) may also influence child outcomes but they were not collected in Project Viva or IFPS II.

Age of egg introduction. At **Project Viva** visits, the age of infant egg introduction was asked at 6-m and 12-m using the same question - “How old was your baby when you first fed him/her eggs”. In the **IFPS II**, mothers reported their infant’s intake of 18 types of foods in the past 7 days through monthly surveys from 2-12 m of infant ages. The question used for infant food intake was - “In the past 7 days, how often was your baby fed each food listed below? Include feedings by everyone who feeds the baby and include snacks and night-time feedings.” “Eggs” were one of the 18 types of foods. Accordingly, we will derive the infant age of egg introduction from IFPS II mothers’ monthly responses to infant egg consumption. Our previous analysis on infant dietary patterns showed that 1.7% and 63.0% of IFPS II infants had been introduced eggs by 6 m and 12 m of age, respectively⁴².

Frequency of egg intake. At the 2-y survey in **Project Viva**, the frequency of infant egg intake in the past month was obtained from the mothers’ response to the question - “Please check the box that best represents how often your child eats each of the foods listed, on average, in the past month”. One of the food items for this question was “Whole eggs”. Response options for the frequency of consuming “Whole eggs” included “never”, “<once/week”, “once/week”, “2–4 times/week”, “nearly daily or daily”, and “≥2 times/day”.

The same question was asked again at surveys at 3 y and 7 y. As mentioned above, mothers in the IFPS II reported their infant's intake of eggs in the past 7 days through the monthly surveys from 2-12 m of infant ages. Infant egg intake was reported as the number of feedings per day or per week. Our analysis on infant dietary patterns showed the mean egg intake among IFPS II infants was 0.01 (SD, 0.10) and 0.27 (SD, 0.37) serving/week at 6 m and 12 m, respectively⁴².

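### The lowest-risk age of egg introduction is read as a point minimum over the whole observed range, although in IFPS II at most about 52 of 3,033 infants had egg by 6 months

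*Combined protocol and SAP*

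**What the plan says.** In section 3, Project Design, the data analysis text on the average probability of multiple child outcomes takes predictions from the logistic models while the exposure "varies across the observed range within our study sample". The selection rule is: "We will identify the lowest-risk infant egg consumption when the corresponding average probability of the 6 adverse outcomes is the lowest". No minimum count, percentile limit or interval accompanies it.

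The Aim 1 categories are "never, <2 m, 2-3 m, 4-5 m, 6-8 m, 9-11 m, and 12 m", so three of seven lie below 6 months. Under Age of egg introduction, the plan reports from an earlier analysis that "1.7% and 63.0% of IFPS II infants had been introduced eggs by 6 m and 12 m of age, respectively". No such distribution is given for Project Viva.

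Hypothesis 2 predicts a non-linear association "with the optimal age being a time point that falls between 6-12 months". The composite uses "6 binary child outcomes including stunting, underweight, obesity, high risk of metabolic syndrome", food allergy and cognitive delay. Metabolic and cognitive measurements are described for Project Viva only.

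**The concern.** A fitted curve returns a value at every age in its range, however few infants are there. A rule that takes the lowest point of the curve can therefore name an age at which almost nobody was introduced to egg, with nothing in the output to warn the reader. The thin part of the range is the part that matters most. The Background frames the debate around introduction at 4-6 months, and Figure 1 leads from the findings to clinical guidelines. A statement that an age before 6 months carries the lowest risk, or that 6-12 months is better than earlier introduction, is the one most likely to be used. In IFPS II it is also the one with the least data behind it.

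**Working it through.** **Inputs from the documents.** IFPS II N = 3,033; Project Viva N = 2,128; IFPS II introduction 1.7% by 6 months and 63.0% by 12 months; detectable odds ratios 1.46 (Viva) and 1.38 (IFPS II) at type 1 error 0.05 and power 0.8 (Statistical Power).

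**Assumptions.** Both percentages apply to all 3,033 infants. Baseline risk is 5% to 20%. Tests are two-sided.

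**Step 1: the plan's own figure.** For two proportions with a pooled-variance test, power = Φ[(|p1 − p2| − 1.96·SE0)/SE1], solved for the odds ratio at 0.8. An equal split of each full cohort and a 10% baseline (both assumed) give 1.458 and 1.376, matching 1.46 and 1.38. The stated figures therefore fit a comparison of two halves of a cohort. The plan's worked example there is ≥12 months against 6-8 months, not introduction before 6 months.

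**Step 2: counts in IFPS II.**
- By 6 months: 0.017 × 3,033 = 51.6, about 52, over three categories.
- From 6 to 12 months: (0.630 − 0.017) × 3,033 = 0.613 × 3,033, about 1,859.
- Not introduced by 12 months: 0.370 × 3,033, about 1,122.

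Of introductions dated by 12 months, 61.3/63.0 = 97.3% fall after 6 months and 2.7% by 6 months. If 80% or 50% of infants were followed to 6 years (assumed), the 52 become about 41 or 26. The plan first analyses boys and girls separately, and an even split of the 52 leaves about 26 per sex.

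**Step 3: what those counts can detect for one binary outcome.** Each comparison is against the 1,859 infants introduced at 6-12 months.

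| Assumed baseline | By 6 m (52), harm | By 6 m (52), protection | Not by 12 m (1,122), harm |
|---|---|---|---|
| 5% | 3.46 | none reaches 80% power | 1.55 |
| 10% | 2.75 | 0.06 | 1.39 |
| 20% | 2.33 | 0.26 | 1.29 |

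The harm column for the 52 bears on showing that 6-12 months is better than earlier introduction. The protection column bears on placing an optimum before 6 months. The Background cites a pooled risk ratio of 0.56 for egg allergy with introduction at 4-6 months. Power to see a ratio of that size in the 52 infants is about 5%, 12% and 31% at baselines of 5%, 10% and 20%.

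**Step 4: does thin support disturb the minimum?** An illustrative simulation used six outcomes, quadratic logistic models and assumed ages and prevalences. With 1.7% of infants introduced early, the standard deviation of the averaged risk at the earliest age was about three times that under even exposure. When true risk fell 3% per month, so that the earliest ages were the worst, the minimum still landed before 6 months in 11% of runs, against 0.5% under even exposure.

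**Step 5: Project Viva.** Its share introduced early is unknown. Shares of 1.7%, 5% or 10% (assumed) would give 2,128 × share = 36, 106 or 213 infants.

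**The case against.** Four objections have force.

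- **The evidence is from one cohort.** The six-outcome average cannot be formed in IFPS II alone, and Project Viva asked age at first egg directly, whereas IFPS II derives it from 7-day intake reports. The 1.7% cannot be carried over. This stands: the finding of thin support is limited to IFPS II, and for Viva the point is a check that has not been reported.
- **A reader might infer that the data cannot refute Hypothesis 2, or confirm it by construction, because 97% of dated introductions fall in its window.** The documents do not support that. The 97% leaves out the 37% not introduced by 12 months. As a share of all IFPS II infants the window holds 61.3%. The 1,122 others form a large group for the categorical comparison, and the fitted minimum can fall outside 6-12 months.
- **A reader might also point to simulations with no true effect, where the minimum falls before 6 months in 44-51% of runs.** That is not evidence of sparsity: even exposure gives 42-43%. It shows what a point minimum does without an interval, and so supports adding one.
- **A percentile limit could itself favour Hypothesis 2.** With only 2.7% of dated introductions by 6 months, a 5th-95th percentile range in IFPS II would lie wholly inside 6-12 months. This stands, and any limit on the range must come with a contrast that can go against the hypothesis.

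The Statistical Power remark that "infant egg consumption varied largely within cohorts" covers frequency and both cohorts as well as age, so the 1.7% does not make it false. It also does not answer the question of support before 6 months.

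**Conclusion.** The concern holds in a limited form. The rule takes a point minimum over an unrestricted range and attaches no uncertainty to its location. In IFPS II at most about 52 infants lie before 6 months, with a detectable odds ratio for harm of about 2.3 to 3.5 instead of the stated 1.38. That cohort cannot reliably locate an optimum there or establish that 6-12 months is better than earlier introduction. The composite rests on Project Viva or a pooled set that the plan does not specify, and support there is unknown. Hypothesis 2 remains open to contradiction. The figures assume a common denominator of 3,033, baseline risks of 5% to 20% and no follow-up loss; loss would make them worse.

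**What to change.** Before outcomes are examined:

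1. Tabulate age of introduction by category in each cohort, and in any pooled set used for the composite.
2. In the average-probability text, replace the observed range with a supported range prespecified from that exposure distribution alone.
3. Merge <2, 2-3 and 4-5 months into one <6 months group. Where support is absent, report it descriptively and do not rank it.
4. Report a bootstrap interval for the location of the minimum.
5. Where the supported range lies inside 6-12 months, test Hypothesis 2 by the contrast of 6-8 months, 9-11 months and not introduced by 12 months. State that a minimum found inside such a range does not count as confirmation.

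The cost is a change of wording, one table from data already held and a resampling step. The downside is that the conclusion covers a narrower range of ages and may say nothing on the ranking of introduction before 6 months.
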